This is a pilot study of a single treatment designed to preliminarily evaluate the effect of psilocybin in patients with cancer and anxiety. Secondary outcome measures will be pain perception, depression, and existential / psychospiritual distress. Also, issues related to the feasibility of using psilocybin in patients with cancer and anxiety will be described. The study will look at both short-term, immediate effects as well longer-term effects. We plan to collect and analyze data up to 6-months post the second drug administration for all enrolled participants. Participants who complete a psilocybin dosing session and agree to be contacted will be invited to partake in two optional data collection time points, which will look at long-term psychological effects of psilocybin-assisted psychotherapy.. Subjects’ participation in these two additional longitudinal timepoints will be optional and will not affect their previous study involvement as research participants. Study participants who opt out or who do not have the option to participate (for example, if they are deceased) will be classified (ie study completers, withdrawn, treatment dropout, etc.) as they were in the main portion of the study. Participants do not need to complete all questionnaires given at previous time points to be eligible to participate in optional time points T13 and T14.

Criteria for patient selection (Inclusion/Exclusion Criteria)

The proposed project will involve up to 47 subjects 18-76 years of age. Subjects will have a current or historical diagnosis of cancer with a projected life expectancy of approximately 6 months or more and a DSM-IV psychiatric diagnosis, as determined by the Structural Clinical Interview for DSM-IV (SCID), of one of the following Anxiety Disorders: Acute Stress Disorder, Generalized Anxiety Disorder, Anxiety Disorder Due to cancer, or Adjustment Disorder with Anxiety. The cancer could be: at any stage of active illness; potentially life

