According to a recent study by Moreno and colleagues, published in 2006, in patients with refractory Obsessive Compulsive Disorder (OCD), an anxiety spectrum disorder, it was found that, with psilocybin, subject's mean YBOCS scores were reduced to 10.67 at 24 hours from 24.11 +/- 6.3 at baseline (Moreno 2006). This represents a reduction of 2 in effect size (assuming a 0.5 correlation between baseline and 24 hours). If we assume placebo has no effect on anxiety, depression and pain, a sample size of 16 subjects in each group (in the first treatment session) will provide 75% power to detect a reduction of 1 effect size, and > 99% power at 2 effect sizes, at the 5% level. This power analysis shows that even if patients dropout before the second cross-over session, the total of 31 patients in the first session will have adequate power for the study endpoints.

Regarding the effect of psilocybin on the outcome variables measuring anxiety, the STAI and HAD scale, analyses will be conducted using a paired t-test to evaluate the effect of treatment over time. The comparisons will be between the following time points: (T0 & T1)-T4, (T0 & T1)-T5, (T0 & T1)-T6, and (T0 & T1)-T7. The comparisons between the active agent and placebo groups will be conducted using an independent sample t-test to look at differences on the STAI and HAD scale measures. Similar analyses will be conducted both within and between groups for the other outcome measures, assessing for depression (POMS-SR, BSI and BDI scales) and pain (BPI-SF, MSAS, and MSKCC scales).

To assess the interaction between drug and time, a series of repeated measures multivariate analyses of variance (MANOVA) will be used to compare the active drug and placebo study arms across time in terms of the major outcome variables during the first and second randomized experimental treatment sessions. Both treatment main effects across time and interactions of treatment with time will be assessed in the repeated measures MANOVA.

Longer-term effects will be measured in two ways looking at the outcome measures of anxiety, depression, and pain. First the effect of time will be assessed with a MANOVA analysis from baseline relative to T7-T12. Also, MANOVA will be used to look at the effect of sequencing of getting the active agent vs. placebo in a sequence x time analysis from baseline relative to T7-T12.

Data Management and Statistics:

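### Within-arm paired t-tests on anxiety are described as evaluating the effect of treatment; the planned between-arm t-test has no precedence over them and no baseline covariate

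*Combined protocol and SAP*

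**What the plan says.** All the analysis text is in the section Statistical Analyses (Including Power Analysis).

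- The anxiety paragraph, on STAI and HAD, opens with the within-arm analysis: "analyses will be conducted using a paired t-test to evaluate the effect of treatment over time". It continues: "The comparisons will be between the following time points: (T0 & T1)-T4, (T0 & T1)-T5, (T0 & T1)-T6, and (T0 & T1)-T7".
- The arm comparison comes next: "comparisons between the active agent and placebo groups will be conducted using an independent sample t-test". The sentence does not say whether follow-up or change scores are compared, and names no covariate.
- Depression and pain follow the same pattern: "Similar analyses will be conducted both within and between groups for the other outcome measures".
- A repeated-measures MANOVA compares the arms over both sessions: "Both treatment main effects across time and interactions of treatment with time will be assessed in the repeated measures MANOVA". A further sequence-by-time MANOVA runs from baseline to T7 through T12.
- No analysis is called primary.
- The power statement is for 16 per group in the first session. It gives 75% power at an effect size of 1 and over 99% at 2, at the 5% level, under this premise: "If we assume placebo has no effect on anxiety, depression and pain". It takes 0.5 as the correlation between baseline and 24 hours in the study of obsessive-compulsive disorder that supplies the effect size.

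**The concern.** A change within one arm is not the effect of the drug. In this trial it can contain:

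- **Placebo response**, which the power statement sets to zero as a premise.
- **Follow-up contact.** Patients have at least three meetings, totalling at least 6 hours, in the first six weeks after a session (Meetings with Study Staff and Monitors Following Treatment Sessions). A growing part of this falls before the later time points.
- **Preparation, where T0 is in the baseline.** At least 6 hours of sessions take place in the 2 to 4 weeks before session 1 (Meetings with Monitors Before Treatment Sessions).
- **Some regression to the mean, on HAD and where T0 is in the baseline**, because a HAD score below 8 at T0 excludes the patient (Criteria for patient selection).

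Change from T1 alone is largely free of the last two. The niacin arm exists to separate all of these from the drug. If the paired tests keep their present description, a significant change in the psilocybin arm can be reported as a treatment effect on the primary outcome when niacin patients improved just as much.

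**Working it through.** **1. The plan's own power figure.** For a two-sample t-test, two-sided 5% (sidedness is not stated, so this is assumed), the noncentrality is d·√(n₁n₂/(n₁+n₂)). At d = 1:

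- 16/16: 2.83, df 30, power 78.1%.
- 16/15, the plan's total of 31: 2.78, df 29, power 76.7%.
- 15/15: 2.74, df 28, power 75.3%.

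A paired test with n = 16 and d = 1 has noncentrality 1·√16 = 4 and power 96.2%. The stated 75% therefore fits the between-arm test in session 1, not the paired test.

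**2. Paired test with no drug effect.** Let δ be the non-drug improvement in SDs of change. The documents give no value, so 0 to 0.5 is an assumed range. With n = 16 the noncentrality is 4δ and the critical value is t = 2.131 on 15 df. Probability of a significant improvement:

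| δ | 4δ | n = 16 | n = 15 |
|---|---|---|---|
| 0 | 0 | 2.5% | 2.5% |
| 0.1 | 0.4 | 5.7% | 5.5% |
| 0.2 | 0.8 | 11% | 11% |
| 0.3 | 1.2 | 20% | 19% |
| 0.5 | 2.0 | 46% | 44% |

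A shift common to both arms cancels in a between-arm test. Simulated rejection rates for the between-arm tests were 4.8% to 5.2%, with or without such a shift.

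**3. Regression to the mean alone, HAD.** Normal scores were truncated at 8 or more at T0, with no effect, n = 16, SD 3 to 4 and correlations 0.5 to 0.8 (all assumed). Significant improvement from the T0/T1 mean occurs in 8–14% of trials if the screening mean is 8, 5–9% at 10, 3–5% at 12 and 3–4% at 14. From T1 alone it stays at about 2.5%. The lower end is more plausible, because entry also requires a diagnosis "of one of the following Anxiety Disorders".

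**4. Power of the between-arm options.** d = 1 raw-score SD, 16/15, two-sided 5%, and T0, T1 and follow-up equally correlated at r. Only 0.5 stands in the plan, and there for another study; 0.3 and 0.7 are assumed. SD of the compared quantity:

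- Follow-up score: 1.
- Change from T1: √(2(1−r)); at r = 0.5 this is 1.
- Change from the T0/T1 mean: √(1+(1+r)/2−2r); at r = 0.5 this is 0.866.
- ANCOVA on T1: residual SD √(1−r²), 28 df, simulated so that chance baseline imbalance is included.

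| Analysis | r = 0.3 | r = 0.5 | r = 0.7 |
|---|---|---|---|
| t-test, follow-up score | 76.7% | 76.7% | 76.7% |
| t-test, change from T1 | 62% | 77% | 94% |
| t-test, change from T0/T1 mean | 75% | 87% | 98% |
| ANCOVA on T1 | 79% | 86% | 96% |

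**5. Unequal correlations.** T0 is earlier than T1 and precedes the preparation, so equal correlations need not hold. Keep T1–follow-up at 0.5, which leaves ANCOVA on T1 at about 86%:

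- T0–follow-up 0.5, T0–T1 0.8: change from the T0/T1 mean has SD √(1+0.9−1.0) = 0.949 and power 80.9%; ANCOVA on that mean has about 87%.
- T0–follow-up 0.3, T0–T1 0.7: change from the mean has SD √(1+0.85−0.8) = 1.025 and power 74.7%, below the plain t-test; ANCOVA on the mean has about 83%.

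So neither change from the T0/T1 mean nor that mean as covariate is reliably better than adjusting for T1.

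**The case against.** The strongest reply is that the plan already has valid tests. The independent t-test follows the paired tests directly, and the MANOVA tests treatment by time. The sequence-by-time MANOVA includes baseline to T7, and T7 at 6 weeks precedes the second session at 7 weeks (plus up to one), so that contrast is a pre-crossover comparison of change between arms. The trial is also a pilot. All of this stands and lowers the severity.

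A reader might infer that the trial lacks a valid test of the drug, or that the plan will declare efficacy from a paired test. The documents support neither. The paired-test sentence speaks of an effect over time and sets no success rule, and the zero placebo effect is a sample-size premise only.

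A reader might also infer that 6 hours of follow-up meetings precede T5 or T6. The plan spreads them over six weeks, and T5 is one day after dosing.

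On precision, the independent t-test may be meant for the differences from T0 and T1 listed just before it. On that reading ANCOVA on T1 may gain nothing, so a fixed gain cannot be claimed.

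Finally, ranking the between-arm comparison does not choose among STAI, HAD and the four time points. That is true, and it is a separate question.

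**Conclusion.** The point holds as a misdescribed and possibly less precise analysis, not as a missing valid test. The paired tests are presented as evaluating treatment, and the between-arm t-test, which matches the power statement, is neither ranked above them nor adjusted for baseline.

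The 5.7% to 46% false-improvement rates rest on assumed non-drug shifts of 0.1 to 0.5 SD of change. Regression to the mean alone would produce much less, and was examined only for HAD. The near-5% rate of the between-arm tests does not depend on these shifts.

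At r = 0.5, ANCOVA on T1 gains about 9 points of power (86% against 77%) over a t-test on follow-up scores or on change from T1. Over r = 0.3 to 0.7 it beats both. Against change from the T0/T1 mean the result can go either way, because the documents do not give the T0 correlations. Severity: minor to moderate.

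**What to change.** In Statistical Analyses (Including Power Analysis):

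1. State that the efficacy comparison is psilocybin versus niacin in session 1, before crossover, by ANCOVA of the post-dose score on treatment with the T1 score as covariate. Apply it to each anxiety scale and time point already listed. Specify the T1 taken before session 1, because T1 is scheduled before each session. T0 may be added as a second covariate.
2. Report within-arm changes as means with 95% confidence intervals and no efficacy p-values, and strike the clause that gives the paired test's purpose as evaluating treatment.
3. Use the same wording for the depression and pain scales. Keep the MANOVA as a supportive between-arm analysis.

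The cost is a text change and one degree of freedom for the T1 covariate (28 instead of 29 with 31 patients). If T0 is added, it takes one more. No new data or visits are needed.

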The primary objective of this double-blind, placebo-controlled pilot study is to assess the efficacy of psilocybin administration (4-phosphoryloxy-N,N-dimethyltryptamine), a serotonergic psychoactive agent, on psychosocial distress, with the specific primary outcome variable being anxiety associated with cancer. Secondary outcome measures will look at the effect of psilocybin on symptoms of pain perception, depression, existential/psychospiritual distress, attitudes toward disease progression, quality of life, and spiritual/mystical states of consciousness. In addition, a secondary objective of the study is to determine the feasibility of administering psilocybin to this patient population, with regards to the following issues: safety, patient recruitment, consent for treatment, and retention. The duration of the proposed investigation will be long enough to administer the drug one time to each of thirty-two patients and to conduct follow-up assessments. This study would be separate but similar to a completed study at the Los Angeles Biomedical Research Institute at Harbor-UCLA Medical Center, run by a psychiatrist, [name], and an oncologist, [name]. Although the outcomes measures would be similar to those used as in the Grob study, the proposed dose of psilocybin would be somewhat higher at 0.3mg/kg and the total number of subjects randomized for the study would be 31 instead of 12 (see below explanation and justification). This study has been approved by the Bellevue Psychiatry Research Committee, the Oncology PRMC Committee, the Food and Drug Administration (FDA) through the issuance of an IND (77,138), the NYU IRB and the NYU-HHC Clinical and Translational Science Institute (CTSI) (previously known as the Bellevue General Clinical Research Center GCRC).

Hypothesis/Potential Mechanism of Action:

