The first attempt to re-study the safety and efficacy of psilocybin in patients with potentially life threatening cancer began in 2004 in a study that is now completed at the Los Angeles Biomedical Research Institute at Harbor-UCLA Medical Center, run by a psychiatrist, [name], and an oncologist, [name]. It was a double-blind placebo-controlled study that included patients with Stage IV cancer and anxiety. The approved oral dosage given of psilocybin was 0.2mg/kg and a total of 12 patients were studied. There were several medical exclusion criteria including renal disease, abnormal liver function tests, epilepsy, and cardiovascular illness, as well as psychiatric exclusion criteria including the presence of major mental illness and active substance abuse. This study was funded by the Heffter Research Institute and was FDA approved. The study had a prospective follow-up arm that followed patients for up to 6 months post-treatment of psilocybin. The study was recently published in the Archives of General Psychiatry in September

2010 (Grob 2010). The results were as follows: ‘Safe physiological and psychological responses were documented during treatment sessions. There were no clinically significant adverse events with psilocybin. The State-Trait Anxiety Inventory train anxiety subscale demonstrated a significant reduction in anxiety at 1 and 3 months after treatment. The Beck Depression Inventory revealed an improvement of mood that reached significance at 6 months; the Profile of Mood States identified mood improvement after treatment with psilocybin that approached but did not reach significance.’ This study established the safety and feasibility of administering a moderate dose of psilocybin to patients with advanced cancer and anxiety. Some of the data suggested a treatment effect with reduction in anxiety and depressive symptoms.

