Treatment efficacy for anxiety and depression will be assessed by the State-Trait Anxiety Inventory (**STAI**), Hospital Anxiety and Depression (**HAD**) scale, Brief Profile of Mood States (**POMS-SR**), Beck Depression Inventory (**BDI**), and Brief Symptom Inventory (**BSI**). The STAI, HAD, POMS-SR, BDI, and BSI will also be re-administered at the following time points: T1, T4-T12. In addition, regarding a broad assessment of affective states, the Positive and Negative Affect Schedule Expanded Form (**PANAS-X**), a 60-item questionnaire, will be administered to assess for positive and negative affect. This scale will be re-administered at the following time points: T6 (2-weeks after drug administration) and T12 (26-weeks after drug administration). The STAI, HAD and BDI will be re-administered at T13 and T14.

Pain

Treatment efficacy for pain perception will be assessed by the Brief Pain Inventory – Short Form (**BPI-SF**), and the Memorial Symptom Assessment Scale (**MSAS**) (only questions relevant to anxiety, depression or pain symptoms) will be administered two weeks prior to the experimental treatment session, the day before, 7-hours after each drug administration session, the day after, two weeks after the session, and then every month for the next six months. In addition, the Memorial Sloan Kettering Pain Card (**MSKCC**) will be self-administered by the subjects every day from two weeks before the treatment session until six weeks after, including just before psilocybin administration and at four and seven hours afterward. Subjects' use of pain medications will be closely monitored throughout the study duration.

Attitudes towards disease progression and death

Attitudes towards disease progression and death will be measured at baseline with the following measures: Death Transcendence Scale (**DTS**), Demoralization Scale (**DEM**), Death Anxiety Scale (**DAS**), and the Hopelessness Assessment and Illness (**HAI**) scale. These measures will also be obtained at the following time points: T6 (2-weeks after drug administration) and T12 (26-weeks after drug administration). The DEM, DAS and HAI will be re-administered at T13 and T14.

Quality of Life/Spirituality:

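### Anxiety is the primary outcome, but no anxiety score, visit or test is named as primary and no multiplicity rule is given

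*Combined protocol and SAP*

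**What the plan says.** The opening summary sets the primary objective as efficacy on psychosocial distress, "with the specific primary outcome variable being anxiety associated with cancer". Depression and pain are listed there as secondary.

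The Anxiety and Depression paragraph of the measures section begins "Treatment efficacy for anxiety and depression will be assessed by the State-Trait Anxiety Inventory" and lists five instruments for anxiety and depression together. Statistical Analyses (Including Power Analysis) narrows anxiety to the STAI and the HAD and plans four kinds of test:

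- Paired t-tests over the contrasts "T0 & T1)-T4, (T0 & T1)-T5, (T0 & T1)-T6, and (T0 & T1)-T7", that is, 7 hours, 1 day, 2 weeks and 6 weeks after dosing.
- Comparisons of active agent with placebo, which "will be conducted using an independent sample t-test to look at differences on the STAI and HAD scale measures". This sentence follows the list of contrasts and is naturally read as covering the same visits.
- MANOVAs over the first and second sessions: "Both treatment main effects across time and interactions of treatment with time will be assessed in the repeated measures MANOVA".
- Longer-term MANOVAs, for time and for sequence by time, from baseline relative to T7 to T12.

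The power statement in the same section says that "a sample size of 16 subjects in each group (in the first treatment session) will provide 75% power" to detect one effect size at the 5% level. Its benchmark is an external study in obsessive-compulsive disorder, in which "mean YBOCS scores were reduced to 10.67 at 24 hours".

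**The concern.** A primary outcome should lead to one result that answers the primary objective. Here it is a construct only. Two instruments, four visits and four families of test could each supply the answer, and nothing ranks them.

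Two further choices are open:

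- **The STAI score.** Rationale and Background reports the earlier cancer study's result on a part of that instrument: the "anxiety subscale demonstrated a significant reduction in anxiety at 1 and 3 months after treatment". So the STAI has at least one part that is reported separately, and the plan selects none.
- **The baseline.** T0 and T1 are bracketed together without saying whether they are averaged or used separately.

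At stake is the reading of the trial. Without a named primary test, a report could rest the efficacy conclusion on whichever score, visit or method gave the clearest result, and a reader could not tell from the plan whether that result was the intended one.

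**Working it through.** **1. The plan's own power figure.** The plan states 75% with 16 per group at one effect size, and above 99% at two. For a pooled two-sample t-test at two-sided 5% (sidedness is not stated, so this is assumed), the noncentrality is d / √(1/n₁ + 1/n₂) with n₁ + n₂ − 2 degrees of freedom.

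| Measured per arm | Noncentrality, d = 1 | Critical t | Power |
|---|---|---|---|
| 16/16 | 2.828 | 2.042 | 78.1% |
| 16/15 (the plan's 31) | 2.782 | 2.045 | 76.7% |
| 15/15 | 2.739 | 2.048 | 75.3% |
| 14/13 (assumed losses) | 2.596 | 2.060 | 70.4% |
| 12/12 (assumed losses) | 2.449 | 2.074 | 64.9% |

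The stated 75% is slightly conservative for 16 per group, and the figure above 99% at d = 2 reproduces (99.97% with 16/15). The selection criteria expect losses from disease progression but give no rate, so the last two rows are illustrations.

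The benchmark is (24.11 − 10.67) / 6.3 = 2.13. With the plan's correlation of 0.5 and equal SDs, the SD of change is 6.3 × √(2 × 0.5) = 6.3, so the plan's rounded value of 2 follows. This is a 24-hour effect on another scale in another disorder. The calculation fits one between-arm test in the first session, but the plan applies it to its endpoints in general and names no scale or visit.

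**2. Counting the between-arm anxiety tests.** Two instruments × four visits = 8. This leaves out STAI parts, paired tests and all MANOVAs.

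**3. Chance of at least one false positive.** If the eight tests were independent it would be 1 − 0.95⁸ = 33.7%. Scores on the same patients are correlated, so this was simulated: 100,000 null trials, 16 v 15 patients, unadjusted two-sided 5% t-tests, any one rejection counted as success.

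| Tests | Correlation 0.5 | 0.7 | 0.9 |
|---|---|---|---|
| One named test | 5% | 5% | 5% |
| Two scores, one visit | 9.1% | 8.5% | 7.1% |
| Eight tests, one common correlation | 25.5% | 19.7% | 12.0% |
| Eight tests, score and visit correlations multiply | 27.0% | 21.5% | 13.2% |
| Eight tests, Holm, common correlation | 4.1% | 3.3% | 1.9% |

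The correlations are assumptions; the documents give none.

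**4. What Holm over eight tests would cost.** The first step uses 0.05 / 8 = 0.00625. With 16/15 and d = 1 the critical t is 2.949 and the power 44.8%. Later steps are easier. If all eight true effects equal 1 SD, simulation (20,000 runs, common correlation 0.5 to 0.9) gives average Holm power of about 54% to 56% per test. The unadjusted figure is 76.7%.

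**The case against.** The plan is less open than a list of its tests suggests. It gives each method a purpose: change over time, active against placebo, and the interaction of drug with time. It narrows five instruments to two for anxiety. Its power statement points to a first-session between-arm comparison with a benchmark at 24 hours, close to T5. This is also a pilot meant for preliminary evaluation, where strict family-wise control is not a given. All of that stands and lowers the weight of the point, but none of it designates a primary result. A pilot may label its tests exploratory; this text does not, while it names a primary efficacy outcome and states power at the 5% level.

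A reader might infer more than the documents support:

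- *The between-arm tests have no visits.* The sentence follows the T4 to T7 list and naturally inherits it.
- *The trial's false-positive rate is 12% to 27%.* That needs a rule that any one significant result is enough, and the plan states no such rule.
- *The power figure is for anxiety.* It is given for the endpoints in general, with no placebo effect assumed on anxiety, depression or pain.
- *The HAD entry cut-off leaves the endpoint undefined.* It is an eligibility rule, and the visible text describes no HAD subscales.
- *The earlier study shows that the answer depends on the score chosen.* The plan reports one positive STAI result from it and no contrasting anxiety result.

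Table 1, cited in the measurements section, is not visible and might specify scores.

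**Conclusion.** The point holds for the visible text. Anxiety is primary as a construct, but no score, visit or test is primary, no multiplicity rule is given and the baseline is undefined. The size is about 12% to 27% for at least one false positive among eight between-arm tests, against 5% for one named test. It rests on 16/15 measured, unadjusted two-sided tests, correlations of 0.9 down to 0.5, and any one rejection being taken as success.

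The gap concerns how the primary objective will be answered. It is not evidence that results were or will be chosen selectively, and pilot status limits the consequence. It is still worth correcting, because the remedy is cheap and the study presents an efficacy outcome with a power figure.

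**What to change.** The remedy depends on whether main-phase outcome data have been seen. The version date of 3.21.18 and the references to study completers and past participants make this likely, but the documents do not say so.

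- **If data have been seen:** do not name a primary now. Label all anxiety tests exploratory, or report Holm-adjusted p-values over the eight between-arm anxiety tests.
- **If they have not, including at the interim efficacy look planned after five completers:** name one anxiety score at one first-session visit from T4 to T7 as the single between-arm primary test at two-sided 5%. The choice is the sponsor's. All four visits fall before the second session, which is at least 7 weeks after the first. State how T0 and T1 form the baseline. Label every other anxiety test, within-arm tests and MANOVAs included, secondary or exploratory. Tie the power figure to the named test: 77% at 1 SD with 16/15 measured.

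The cost is a short addendum, with no extra patients, visits or data. With a single primary, a positive result on another score or visit becomes secondary evidence. With Holm, power per test at 1 SD falls from 77% to 45% at the first step, or about 54% to 56% on average if all eight effects equal 1 SD. If data have been seen, neither option restores pre-specification.

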It is hypothesized that a one time experience with psilocybin will occasion significant shifts in consciousness and awareness that will lead to short-term (i.e. hours to days) and long-term (up to 5 years in this study following the second experimental session) improvement in anxiety, depression, and pain associated with cancer. The exact mechanism of action is unclear but based on studies conducted with similar serotonergic agents in patients with advanced cancer, improvements in anxiety levels, mood and pain were reported (Grob and Halifax 1977; Kast 1970). However, a treatment model developed by the British psychiatrist, Humphrey Osmond, offers one possibility. In this model, serotonergic hallucinogens' therapeutic mechanism lies in their ability to allow the individual to access novel dimensions of consciousness and their efficacy or lack thereof relies on whether a significant reappraisal or alteration in perception is attained (Osmond 1957). Another possible mechanism relates to what Dobkin de Rios and Grob have described as 'managed altered states of consciousness,' where the power of suggestibility, occurring in a safe setting, allows one to transcend a particular state of consciousness (i.e. anxiety and depression associated with cancer) as a means to facilitate emotional discharge and to manage irreconcilable conflict (Dobkin de Rios, Grob, & Baker 2002).

Rationale and Background:

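### The drug-versus-placebo MANOVA covers both crossover sessions with no carryover, period or sequence term, no named baseline and no rule for which session governs, although the protocol expects benefit to outlast the gap

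*Combined protocol and SAP*

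**What the plan says.** All of the analysis text is in the section Statistical Analyses (Including Power Analysis).

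- **MANOVA.** "To assess the interaction between drug and time, a series of repeated measures multivariate analyses of variance (MANOVA) will be used" to compare the active and placebo arms on the "major outcome variables during the first and second randomized experimental treatment sessions". The effects to be tested are: "Both treatment main effects across time and interactions of treatment with time will be assessed in the repeated measures MANOVA". No other term, no baseline and no combination rule is given.
- **Between-arm t-test.** "The comparisons between the active agent and placebo groups will be conducted using an independent sample t-test". The session is not named.
- **Power.** "a sample size of 16 subjects in each group (in the first treatment session) will provide 75% power" for a reduction of 1 effect size. The section adds that the 31 first-session patients suffice even if some drop out before the second session.
- **Order of treatment.** A separate long-term MANOVA looks at sequencing in a "sequence x time analysis from baseline relative to T7-T12".

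Under Materials and Methods and Drug Conditions, the sessions are 7 weeks (+ 1 week) apart, and the interval is not described as a washout. The Hypothesis section expects "long-term (up to 5 years in this study following the second experimental session) improvement in anxiety, depression, and pain". Rationale and Background reports that the predecessor cancer study, at a lower dose, "demonstrated a significant reduction in anxiety at 1 and 3 months after treatment" on the trait anxiety subscale. Under Observations and Measurements, T1 is taken the day before the sessions and T7 is 6 weeks after drug administration.

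**The concern.** In a crossover, the session 2 drug-placebo contrast is clean only if the session 1 treatment has stopped acting. Here the protocol hypothesises the opposite. If it is right, the session 2 placebo data come from patients who still benefit from psilocybin, and a contrast that uses those data measures something smaller than the drug effect unless the model or the baseline allows for it.

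Two things are at stake. One is the effect estimate, which is a main product of a pilot meant to evaluate the effect preliminarily. The other is that several defensible analyses fit the text. With no rule for which one counts, the choice could follow the results.

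**Working it through.** **Inputs from the documents.** Allocation is 16 and 15 (Drug Conditions gives 15 or 16 per group; 31 in total). The level is 5%, and two-sided is assumed because the sidedness is not stated. The effect is d = 1 SD as in the power statement. The plan's cited effect is (24.11 − 10.67)/6.3 = 2.13, which it rounds to 2.

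**Assumptions not in the documents.** The carryover fraction is varied from 0 to 1. The between-session correlation is 0.5. The plan uses 0.5 only for baseline to 24 hours.

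**1. The plan's own figure.** Two-sample t-test, noncentral t, d = 1: 78.1% power for 16/16, 76.7% for 16/15 and 75.3% for 15/15. At 2 effect sizes with 16/16 it is 99.98%. The stated 75% is slightly conservative for 16 per group and close to the value for 31 patients.

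**2. Expected contrasts.** Let a be the fraction of d remaining at the session 2 T1 in the psilocybin-first group, and c the fraction remaining after the session 2 dose. Session 1 estimates d. Session 2 estimates:

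- post-dose scores or change from T0: d(1 − c)
- change from the mean of T0 and that session's T1: d(1 − c + a/2)
- change from that session's own T1: d(1 − c + a)

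An equal-weight pooled contrast is the average of d and the session 2 value. With d = 1:

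| a, c | Pooled, post-dose or T0 | Pooled, mean of T0 and T1 | Pooled, own T1 |
|---|---|---|---|
| 0, 0 | 1.00 | 1.00 | 1.00 |
| 0.5, 0.5 | 0.75 | 0.875 | 1.00 |
| 1, 1 | 0.50 | 0.75 | 1.00 |
| 0.5, 0.25 | 0.875 | 1.00 | 1.125 |

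A 20,000-run simulation (16/15, correlation 0.5) gave 0.752, 0.502 and 0.874 for the post-dose column and 1.003, 1.002 and 1.124 for the own-T1 column in the last three rows.

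**3. One MANOVA per session.** Session 1 is unbiased. The power of a two-group test on session 2 post-dose scores, 76.7% with no carryover, falls to 52.3%, 27.0%, 10.3% and 5% at c = 0.25, 0.5, 0.75 and 1. The two sessions are then expected to disagree whenever benefit persists.

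**4. Cost of leaving the choice open.** With no drug effect (16/15, correlation 0.5, simulated), declaring success on the best of session 1, session 2 and the crossover contrast gives about 12% false positives at a nominal 5%.

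**5. Precision.**

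- Session 1: SE = √(1/16 + 1/15) = 0.359 SD.
- Crossover: SE = 0.5 × √(2(1 − 0.5)(1/16 + 1/15)) = 0.180 SD.
- Crossover power on post-dose scores at d = 1: 99.7%, 98.1%, 91.9% and 76.7% at c = 0.25, 0.5, 0.75 and 1.
- The pooled bias is dc/2, so the crossover has the lower root mean squared error (RMSE) while dc/2 < √(0.1292 − 0.0323) = 0.311. That is c below about 0.62 at d = 1, or about 0.31 at d = 2.

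**The case against.** **The two-session contrast may be the better estimator.** At partial carryover it has more power than session 1 alone and, up to the thresholds above, a lower RMSE. This stands: preferring session 1 is a choice of low bias over precision, and the documents do not fix c. It does not excuse leaving the choice unstated.

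**The text may already separate the sessions.** A series of MANOVAs can mean one per session. It can also mean randomised sequence groups followed through both sessions, where carryover shows as part of the time profile and the pooled formula does not apply. Both readings are possible. Neither says which result answers the drug-versus-placebo question.

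**The sequence analysis is a safeguard.** It is a partial one. It examines order over the long-term data and neither corrects nor governs the two-session contrast.

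Three stronger readings are tempting but not supported:

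- *Every between-arm comparison is contaminated.* The power statement implies a session 1 t-test, and an independent-sample test does not suit pooled sessions in which each completer appears under both conditions. The t-test needs only an explicit statement.
- *The effect could be grossly overstated.* Upward bias needs an own-T1 or averaged baseline and carryover that fades between T1 and follow-up. A 50% overstatement needs full benefit the day before the niacin session and none after it, which fits poorly with the persistence the protocol cites.
- *Carryover itself creates false positives.* With no drug effect nothing carries over. The inflation comes from the open choice.

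**Conclusion.** The concern holds for the MANOVA and should be fixed. Under stable carryover, the pooled estimate on post-dose scores or change from T0 is d(1 − c/2): 25% low at c = 0.5 and 50% low at c = 1, the extreme. With each session's own T1 as baseline it is unbiased. It is 12.5% high if carryover falls from 0.5 to 0.25 between T1 and follow-up. So both the size and the direction of bias rest on choices the plan does not make, and on a carryover fraction the documents do not give. The omission itself does not depend on any value of c. The pooled figures assume equal weighting, and the 12% and the crossover precision assume a between-session correlation of 0.5.

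**What to change.** - State that the session 1 (pre-crossover) between-arm comparison, at time points through T7, is the governing drug-versus-placebo analysis for the MANOVA. Say explicitly that the independent t-test is also limited to session 1.
- Define the baseline from pre-session-1 data: the mean of T0 and T1, or one of them. The paired t-tests cite T0 and T1 together without saying how they combine, so that needs defining too.
- Report session 2 by sequence as secondary. If a two-session model is kept, give its period and sequence terms, its baseline and how the sessions are combined.
- If results have been seen when the choice is made, disclose it. The document is dated 3.21.18, and the text on the optional time points already refers to study completers.

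No visits or patients are added, because T7 at 6 weeks falls before the second session at 7 to 8 weeks. The cost is precision: an SE of 0.36 SD against 0.18 SD, and at d = 1 about 77% power against about 98% at c = 0.5 (equal at c = 1). Session 1 is still preferable because persistent benefit is the protocol's own hypothesis and the power statement already rests on that session.
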